Title: Use of joystick-operated ride-on toys to improve affected arm use and function in children with hemiplegic Cerebral Palsy

NCT #: NCT05559320 Document date: 03/07/2024

SECTION B: OUTLINE OF PROPOSAL

SYNOPSIS/ABSTRACT

Cerebral palsy (CP) is the most common childhood-onset motor disability. It refers to a group of complex, neurodevelopmental disorders of movement and posture due to non-progressive damage to the growing brain leading to significant activity limitations and participation restriction, and frequently accompanied by impaired sensation, perception, cognition, communication, behavior, and secondary musculoskeletal problems.¹ Around 30% of children with CP have hemiplegia, with impairments predominantly lateralized to one side of the body.² As a result of impaired strength/control on the more-affected side as well as difficulties with bimanual coordination (i.e. ability to use both arms together), affected children struggle with even the most basic activities of daily living: feeding, self-care, grooming, school-work, and play.³⁻⁵ Limited use of one side leads to early maladaptive neural and musculoskeletal changes that contribute to "**learned nonuse/disuse**" on the affected side that is difficult to reverse.⁶⁻⁸ Moreover, lost movement opportunities in early childhood likely have cascading negative effects on a child's overall cognitive, perceptuo-motor, social, and emotional development.⁷ The debilitating impact of CP on children's function, the associated economic burden on the health care system, and strong evidence for improved motor outcomes following early movement training together **underscore the importance of early and effective motor interventions in CP**.⁸⁻¹⁰

Contemporary evidence-based approaches to improve UE function such as Constraint Induced Movement Therapy (CIMT) and Bimanual Training (BT) while being effective rely on intense, repetitive practice of functional tasks.¹¹⁻¹³ Despite positive effects of contemporary approaches^{6,13-19}, these programs are very time-consuming, children frequently find activities to be boring and monotonous, training-related improvements are relatively short-term, and evidence for these approaches is often mixed.²⁰⁻²³ Clinicians frequently struggle to retain child interest, ensure therapeutic compliance, and promote functional affected UE use beyond therapy sessions.²⁴ Motivation is the single most influential factor unrelated to the child's diagnosis that determines changes in motor skills, function, and neural reorganization following therapeutic interventions in CP.²⁵⁻²⁷ Compared to healthy peers, children with CP have lower motivation and are more reluctant to try complex, challenging tasks during play.^{26,28} Lack of motivation can limit a child's willingness to engage in activities with the necessary frequency and intensity needed to make functional gains. There is a pressing need for developing stimulating therapeutic environments that provide abundant opportunities to participate in child-preferred, highly enjoyable, intrinsically motivating, and optimally challenging goal-oriented activities to enhance engagement, active practice, and ultimately functional success.^{10,29,30}

We propose to conduct a pilot study to evaluate the efficacy of a home-based, child and familycentric training program using modified commercially-available, joystick-operated, ride-on-toys to improve UE function in children with hemiplegic CP. Home-based programs have been used in children with CP to increase skill practice beyond therapy sessions, improve caregiver involvement in therapy, and facilitate retention of learned skills.³¹ Given the continual challenges faced by clinicians to maintain children's motivation during therapy and ensure repetitive UE practice to induce neuroplastic changes, commercially available, joystick-operated powered ride-on-toy technologies can be adapted and incorporated into home programs to serve as innovative, child-friendly solutions to boost self-initiated UE use in children with impaired arm function. Our pilot data suggest that healthy children as young as 3 years learn to successfully control and navigate a ride-on-toy using joysticks following a brief 5-minute exploratory play period. Children find the experience very enjoyable, and with repeated practice, improve their accuracy of navigation (reduction in average and maximal deviation from optimal central path, number of path deviations, and percent distance spent outside the path).

In a second pilot study, our team provided the ride-on-toy training as part of an existing CIMT-based summer camp for children with hemiplegic CP. Eleven children received training 15-20 minutes/day, 5 days/week for 3 weeks. Training encouraged self-initiated use of the affected arm to move the joystick to navigate through obstacle courses and scavenger hunts. We found strong evidence for feasibility of program implementation and high participant motivation. Children immensely enjoyed the goal-oriented training and key stakeholders (children, clinicians and caregivers) universally reported that the experience was fun and childfriendly. Around 90% of caregivers and 75% of clinicians reported observable improvements in children's arm function (gross motor, fine motor, and bilateral coordination) and spontaneous use following the ride-on-toy training. Camp staff and caregivers indicated that the training was innovative, fun, built confidence in children, and encouraged them to use their affected UE without seeming like "work". However, the inherent design of the camp did not allow us to tease apart the differential effects of the ride-on-toy training versus those of the other regular camp activities. The proposed study will address this gap by exploring the utility of a homebased, incrementally-challenging training program that incorporates ride-on-toy navigation, as an adjunct to conventional UE rehabilitation in children with hemiplegic CP. Our premise is that joystickoperated, ride-on-toys can serve as effective, low-cost, easy-to-use adjuncts to conventional therapy that can be used by both clinicians and families to incentivize affected arm practice during enjoyable navigation-based activities in natural environments, ultimately leading to gains in manual function in children with hemiplegic CP.

BACKGROUND/RATIONALE

The World Health Organization (WHO) has identified CP as having the highest global burden of disease among all non-communicable diseases. It is one of the three pediatric-onset conditions included as part of WHO's "Rehabilitation 2030: A Call to Action" initiative aimed at developing a package of rehabilitation interventions to be part of 'Universal Health Coverage', a strategic WHO priority aligned with the Sustainable Development Goal 3 of the United Nations.^{32,33}The healthcare costs per year for children with CP are estimated at \$6 billion, and additional non-reimbursed costs incurred by families for adaptive equipment, services, and lost income run into thousands of dollars.³⁴ Despite the debilitating impact of CP on the society, a recent systematic review indicated a lack of clinical practice guidelines related to rehabilitation therapies for CP and a disproportionate emphasis of existing programs on remediating impairments in body structures or function rather than on enhancing activities of daily living, participation, and quality of life for children and families.³² There is a pressing need to develop evidence-based, effective, child-centric, and family-engaging interventions to promote function and participation in children with CP.

Around 60% of children with CP have impaired upper extremity (UE) function relative to reach, grasp, release, and manipulation of objects.^{35,36} Limited hand use is the strongest predictor of limitations in daily function and participation in CP and is one of the most challenging rehabilitation goals for clinicians.^{37,38} A variety of interventions including task-oriented approaches such as CIMT^{21,22} and BT³ have been tested to assess effects on UE function^{-7,17-20,23,39,40}. However, the single most critical factor associated with improved clinical outcomes is treatment dose (i.e. optimal, repetitive task practice) rather than the content of any particular treatment paradigm.^{16,20,41,42} Therapists acknowledge that achieving the optimal, intensive treatment dose per existing evidence-based guidelines is most challenging in clinical practice.¹⁸ This may be related to needed therapist expertise to deliver specific types of interventions and associated issues of availability, cost, time, and accessibility.^{17,43,44} Hence, there is growing emphasis on exploring the effects of home programs and the role of caregivers as co-therapists as a pragmatic, cost-effective adjunct or alternative to conventional service delivery models.^{17,20,41,43,45,46} Such programs allow skill practice in naturalistic environments, boost training intensity to exploit brain plasticity, facilitate transfer/retention of learned skills outside the clinic, and foster family involvement through collaborative researcher-caregiver partnerships.^{31,47,48}

Another major barrier to rehabilitation with regard to reaching optimal dosing is child compliance and lack of motivation.^{49,50} **Child motivation is a strong clinician- and caregiver-identified predictor of therapeutic improvements in children's physical and psychosocial functioning.**^{23,51,52,} Although repetitive, goal-directed practice is key to functional success in CP, children frequently find conventional programs boring.⁵³⁻⁵⁶ Therapists must develop activities and create environments that are stimulating, fun, challenging, meaningful, and intrinsically motivating for children, to maximize their engagement and compliance.^{26,50} Higher child motivation will ensure greater active participation in rehabilitation, more practice, enhanced learning, and functional gains.⁵⁰ Contemporary motivational theories, including the Self Determination Theory and Expectancy Value Theory, also suggest that individuals are likely to persist with activities that are age-appropriate and intrinsically rewarding, foster autonomy and a sense of initial achievement/competence, afford social interactions, and provide the "just-right challenge".^{50,57-59}

The above review highlights that achieving the optimal treatment intensity and enhancing motivation and compliance with therapy are the major barriers faced in UE rehabilitation in children with hemiplegic CP. There is an urgent need to develop novel training paradigms that align with child interests, are intrinsically rewarding, encourage intense functional task practice, and involve caregivers, to ultimately enhance child outcomes.⁶⁰⁻⁶² The proposed study, based on principles of motor learning and motivational theories, evaluates the effects of a 6-week, home-based, child-friendly, innovative program that uses modified, commercially available, joystick-operated, powered ride-on-toys to promote spontaneous affected UE use and function in children with hemiplegic CP. Ride-on-devices are very popular toys for children with and without disabilities.^{63,64} The proposed project is highly innovative in the following ways: (1) we will adapt and customize commercially-available toys to individual children's postural control, safety, and arm control needs, (2) we will capitalize on children's intrinsic motivation for mobility and navigation to promote repetitive self-initiated arm use (gross arm movements and fine motor activities) through an incrementally-challenging training protocol grounded in motor learning and motivational theories, (3) the functional mobility training through real physical spaces will provide children with tangible, 3D real-world perceptual, action-related, and cognitive challenges, (4) training will be designed to promote active learning, problem solving, UE movement planning, and sensorimotor integration while providing immediate feedback and consequences of actions,⁶⁵ and (5) we will implement a researcher-caregiver co-delivered home-based intervention to facilitate training carryover into children's daily routines while allowing caregivers to receive ongoing coaching, feedback, and support from clinician researchers.

SPECIFIC AIMS

This proposal introduces an innovative, child-friendly, family-centric, home-based training program to promote UE function in 3-8-year-children with hemiplegic CP through goal-oriented games and activities that incorporate purposeful, joystick-controlled navigation of real-world physical spaces using modified, commercially-available ride-on-toys. Fifteen children with hemiplegic CP will be assessed at 3 time-points: (a) at pretest, (b) at the end of a 6-week, treatment-as-usual/conventional therapy control phase, and (c) at the end of a 6-week experimental intervention phase. The experimental intervention will involve an incrementally challenging training program that will incorporate **Ride-on-toy Navigation Training (RNT)** with joystick controls provided on the child's affected side. Training activities will involve navigational challenges that will require gross motor UE movements (shoulder, elbow, and wrist movements to move the joystick in different directions – forward, backward, left, and right) and include fine motor activities (grasp and control the joystick, pick up/pull/push/throw props, lift and manipulate different types of props like koosh balls, bean bags, cups, blocks, etc. during navigational games). Training activities will be progressed weekly to increase the navigational challenge (straight path, circular path, slalom path, mazes, obstacle avoidance tasks, timed challenges, etc.) and the movement control challenge (increase in required range of UE movements, muscle force control, and manual dexterity for completion of tasks). Children will continue to receive conventional therapy during this intervention phase.

Specific Aim 1: Treatment feasibility and acceptance. To assess treatment feasibility, adherence, fidelity, and satisfaction with a 6-week, researcher-caregiver co-delivered, home-based, training program using ride-ontoys for children with hemiplegic CP, based on child and family feedback. We hypothesize that children will find the experimental intervention phase more enjoyable than the control phase. The training will be acceptable to the family (children and caregivers), feasible to implement for both researchers and caregivers, and associated with high rates of treatment adherence, fidelity of implementation, perceived satisfaction, and perceived benefit as assessed using child- and caregiver-rated questionnaires.

[figure not shown]
Specific Aim 2: Manual function. To evaluate the effects of the training program incorporating ride-on-toys on manual abilities and spontaneous use of the affected arm in children with hemiplegic CP as measured using standardized tests and objective/kinematic measures.

- Aim 2A: We hypothesize that there will be greater improvements in affected arm active movement control and spontaneous functional use as assessed using standardized tests (Quality of Upper Extremity Skills and Shriner's Hospital Upper Extremity Evaluation) and a parent-rated questionnaire (ABILIHAND-Kids), following the intervention phase compared to the control phase. During the intervention phase, children will also show improvements in movement control and maneuverability of the ride-on-toy from an early to a late training session.
- Aim 2B: We hypothesize that children will also show improved motor control and movement kinematics during reaching in terms of increased movement speed, smoothness, straightness, and symmetry, decreased movement variability, and improvements in peak and average velocity of reaching. Children will also show greater improvements in daily arm activity measured through objective wrist-worn activity monitors during the intervention compared to the control phase.

Clinical Impact: This project, led by an early career investigator, strategically leverages the expertise of an interdisciplinary team that comprises experts from physical therapy, occupational therapy, and biomedical engineering who are well suited to implement the proposed project. Our work aligns with the strategic plan of the AACPDM in (1) embracing innovative approaches to advance knowledge and practice in the field of CP and (2) fostering research that will generate new knowledge and evidence to inform care of people with CP. The proposed research will provide evidence to support an innovative, child-friendly, low-cost, home-based training program using commercially-available ride-on-toys that can be implemented by clinicians and families to promote spontaneous, self-initiated practice using the affected UE and improved manual function in children with hemiplegic CP.

RESEARCH METHODS/PLANS

1. Study design: Single group longitudinal design. Children will be observed for a 6-week control phase (conventional treatment-as-usual) followed by a 6-week experimental phase (conventional therapy + RNT).

2. Participants and screening procedures: Fifteen children with a diagnosis of CP, ages 3-8 years with clear asymmetry in UE strength/control will be recruited. Exclusion criteria include a recent history (< 6 months) of trauma/surgery to their UE, inability to sustain supported sitting for 15-20 minutes, blindness/visual impairment, fixed musculoskeletal deformities of the affected hand/wrist, no active control of the affected UE to allow at least brief activation of the joystick to move the toy, inability to follow 2-step verbal instructions, or weight that exceeds the limits of the ride-on-toy. At pretest, we will assess the child's use of their affected hand using the Manual Ability Classification System (MACS).⁶⁶

3. Toy modification & retrofitting phase: Commercially available ride-on-toys come with 2 joysticks. The researchers will modify the toys to: (a) enable operation in a single joystick mode, (b) provide extra postural support (protective outer frame), (c) add a remote-controlled emergency stop, and (d) add sensors to collect toy use and motion data (speed, total time in operation, and motion path) to track the child's navigation efforts.
 4. Testing protocol: Aim-wise primary and secondary measures are listed below:

4.1. Aim 1: The following measures will be used to assess treatment feasibility and acceptance -

1. Primary: Adherence – The toy will collect data on amount of use during training. Researchers and caregivers will also maintain logs during the intervention phase to document training duration and child engagement. 2. Primary: Treatment satisfaction and engagement - Children will complete the valid and reliable, 16-item Physical Activity Enjoyment Scale (PAES) to rate their experience.⁶⁷⁻⁶⁹ Training sessions (one early, mid, and late session each) will be video-coded for child affect (i.e., smile rates, % duration of positive/interested and negative affect) and attention (i.e., % duration of attention to task-relevant targets). Children and/or caregivers will fill out exit questionnaires to assess training satisfaction, enjoyment, repeatability, and caregiver burden. 3. Primary: Treatment fidelity – An unbiased coder will randomly code video data (one each of early, mid, and late sessions) from researcher-delivered sessions using fidelity checklists to assess adherence to the training protocol. Trainers will also fill out posttest exit questionnaires to assess ease of implementation of RNT. 4.2.1. Aim 2A: Manual abilities and spontaneous affected UE use will be assessed as follows -1. Primary: Quality of Upper Extremity Skills Test (QUEST)⁷⁰– This criterion-referenced reliable and valid test assesses UE movement quality using unimanual items scored on a dichotomous scale in 4 domains: grasp, dissociated movement, protective extension, and weight bearing. The scale is valid up to 12 years of age.⁷¹ 2. Primary: Shriner's Hospital Upper Extremity Evaluation (SHUEE)⁷²– This video-based valid and reliable test assesses affected UE use spontaneously and on tester demand in 16 bimanual tasks in 3-18-vear-old children. It has 3 parts: spontaneous functional analysis, dynamic positional analysis, and grasp-release analysis. 5. Secondary: Navigation control and accuracy – Early & late training sessions will be coded for (1) % duration of assisted (child needs trainer-provided manual assistance) versus independent navigation, (2) average duration and number/session of child-initiated, movement bouts normalized by driving time (a bout comprises 1 acceleration and 1 deceleration phase), and (3) rates/session of path deviations and obstacle bumps. 4. Secondary: ABILHAND-Kids⁷³– This valid and reliable parent-rated questionnaire rates the child's difficulty level (3-point ordinal scale of 'impossible', 'difficult', or 'easy') in performing 21 bimanual skills independently. 4.2.2. Aim 2B: 1. Primary: Kinematic measures – Data will be collected during a unilateral and bilateral reachgrasp task at self-selected speed involving different objects (foam ball, rattle, and square block) placed at half arm's length (near) and at arm's length (far) on the table. Sensors (Inertial Measurement Units (IMUs)) will be placed on both hands, both forearms, both arms, and the C7 spinous process. We will assess the speed. smoothness, variability, and symmetry of reaching trajectories. Kinematic and motion data will also be obtained during weekly researcher-delivered training sessions and through toy-mounted sensors. 2. Secondary: Arm activity – Wrist-worn Actigraph activity monitors will be worn during first and last week of

control and intervention phases to assess changes in daily arm activity over the course of the study. **5. Training protocol** – Children will continue to receive conventional therapy such as physical and occupational therapy throughout the study. During the first 6-week control phase, researchers will keep track of conventional therapy received (frequency, duration/session, type) on a weekly basis through parent interviews/training logs. In the second 6-week intervention period, in addition to conventional therapy, children will receive ride-on-toy navigation training (RNT). Researchers will provide 2 sessions/week and caregivers will provide 2 sessions/week each lasting 20-30 minutes. Training will occur at the child's home/school/community spaces like YMCA, playground, etc. Families without access to such spaces will have the option to visit the PI's lab for training. The toy can be driven on different surfaces, e.g., wood, grass, concrete, carpet, etc., allowing for flexibility in accommodating unique space-related constraints faced by families. During weekly visits, researchers will coach caregivers for caregiver-provided sessions. Trainer will fill out training diaries to log details of intervention delivery and child progress. Children will use only their affected arm to move the joystick and the unaffected arm will be enclosed in a soft restraint to encourage use of the affected side during RNT. Each session will include periods of "free play" (child can navigate freely through their physical environment using toy) and "structured play" (child will participate in multi-directional navigation games such as shape mazes, treasure hunts, and obstacle courses). The intervention is based on the motor learning- and familycentric practice-based training principles: variable and repetitive practice, progressive challenges tailored to child needs, activities promoting problem-solving and trial-and-error learning, immediate visual and auditory feedback, playful exploration, incorporation of child-preferred toys/themes into games to increase motivation, and involvement of caregivers and siblings during training. Training will emphasize active UE control of the joystick for starting and stopping the toy, moving steadily forward and backward, turning to the right and left, 180° and 360° turns on both sides, and avoiding obstacles. Activities will also involve small toys/props to encourage gross and fine motor movement and control of affected UE. Trainers will follow a least-to-most prompting hierarchy involving gestural, verbal, and finally hand-on-hand assistance per the child's needs during training. **6.** Project timeline – Please see detailed study timeline below.

Proposed study activities	Year 1	Year 2			
(Q indicates Quarter)	Oct - Dec	Jan-Mar	Apr-Jun	Jul-Sep	Oct-Dec
Intervention development and IRB Approval					
Ride-on-toy modifications and retrofitting					
Recruitment					
Testing/training: Round 1 (5 children)					
Testing/training: Round 2 (5 children)					
Testing/training: Round 3 (5 children)					
Data analysis					
Data dissemination & preparation for R21/R34 grant					

7. Dependent variables and Statistical analyses - For all coded video data, 2 independent coders will rate 20% of the data to establish inter- and intra-rater reliability of over 90%. Standardized tests will be compared between control and intervention phases, training-specific measures will be compared between early, mid, and late training sessions. All kinematic and activity data will be post-processed using custom MATLAB programs. Dependent variables from pretest-mid-point-posttest measures include: (a) total unilateral scores from affected and unaffected sides on sub-tests of the QUEST, (b) total and % scores on sub-sections on the SHUEE, (c) bilateral range of motion, maximum joint angles, peak and average velocity, total movement time, number of movement units, movement straightness, movement variability, and smoothness (e.g. jerk, dimensionless jerk, and log dimensionless jerk)^{74,75} during kinematic tasks, and (d) raw scores on the ABILHAND-Kids and PAES questionnaires. Dependent variables for training-specific measures include: (a) rates of smiles and % duration of positive/interested versus negative affect. (b) % duration of assisted and independent mobility. (c) number and duration of movement bouts during navigation using the ride-on-toy, (d) outcomes derived from kinematic data (as listed in point (c) above) during the training-specific navigation test, and (e) activity counts collected from activity monitors. All data will be evaluated for assumptions of parametric statistics and general or generalized models will be selected accordingly. Variables that violate distributional assumptions of normality will be analyzed using generalized linear model (GLM) procedures, which enable the use of non-Gaussian error models. We anticipate limited missing data because attrition rates are typically low in home-based versus clinic-based programs.^{76,77} When applicable, missing data will be evaluated to determine if it is completely at random. If random, multiple imputation by maximum likelihood estimation will be used.⁷⁸

8. Power analysis – Being the first study to assess effects of ride-on-toy training on UE function in CP, we do not have prior effect size estimates for outcome measures. Therefore, our sample size estimates are derived based on large-sized effects detected in studies that aimed to improve UE function in CP using (a) innovative games such as virtual reality and video games and (b) home-based conventional therapy programs. Effect size estimates in these studies varied from 0.83-1.16 in favor of the intervention group.^{46,79,80} Considering sources (a & b) and our data collection plan, we determined sample size estimates assuming fixed-effects analysis of variance on a 1x 3 design, 1 group and three time points. The study will include a total of 15 cases. The criterion for significance (alpha) has been set at 0.05 (two-tailed). The effect size estimate is 0.80, which yields power of 82% in the most conservative scenario of the effect size estimates we found in the literature.

PROPOSED INVESTIGATORS/SITES AND CONTRIBUTIONS

[name] (PI) is a pediatric physical therapist (PT) with significant experience over the past 12 years in developing novel, creative movement interventions for children with disabilities and working as part of interdisciplinary teams of engineers, designers, and health professionals to develop assistive technologies for children. She also has expertise in designing and conducting clinical trials in patient populations specifically in children with developmental disabilities. [name] will be responsible for project supervision and coordination of the study. She will be responsible for maintaining all study activities including recruitment, data collection, data analyses, and reporting. She will work closely with the Co-Is on all aspects of the study. She will be involved in intervention development and behavioral outcome assessments. She will also leverage her professional networks and alumni connections from the Doctor of Physical Therapy program at the University of Connecticut to assist with participant recruitment. [name] will work with and oversee efforts of graduate and undergraduate students in her lab to train them on procedures related to participant screening and consent, data collection, data coding, and data analyses. She will also oversee ongoing procedures throughout the duration of the study related to ensuring fidelity of data collection and data coding methods.

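### The Aim 2A early-to-late comparison of driving skill is coded from training sessions that are made harder each week, so it mixes skill gain with task difficulty.

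*Combined protocol and SAP*

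**What the plan says.** **Hypothesis.** Aim 2A states that during the intervention phase "children will also show improvements in movement control and maneuverability of the ride-on-toy from an early to a late training session".

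**Measurement.** Section 4.2.1, under the secondary outcome on navigation control and accuracy, says "Early & late training sessions will be coded for" three things: the percentage of time driven with and without manual help; "average duration and number/session of child-initiated, movement bouts normalized by driving time"; and "rates/session of path deviations and obstacle bumps".

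**Task.** The Specific Aims say "Training activities will be progressed weekly to increase the navigational challenge (straight path, circular path, slalom path, mazes, obstacle avoidance tasks", and the list goes on to timed challenges. The demands on arm movement, force control and dexterity rise alongside. Section 5 lists "progressive challenges tailored to child needs" among the training principles, allows different driving surfaces, and lets a session last 20 to 30 minutes. It also puts both free play and structured games in every session.

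**Analysis.** Section 7 compares training-specific measures across early, mid and late sessions. It attaches kinematic outcomes obtained "during the training-specific navigation test", but does not describe that test. Assistance and bouts appear there as separate items. Deviations and bumps do not appear in the section 7 list at all.

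**The concern.** A before-and-after comparison of skill needs the task to stay the same, or its difficulty to be measured and allowed for. Here the task is changed on purpose between the two measurements, in the direction that produces more errors and more need for help. A child who drives better in week 6 than in week 1 may still bump into more things, because week 6 has more to bump into. If training is pitched to keep each child suitably challenged, observed change is also pulled toward zero whatever the child has learned.

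What is at stake is the driving-skill hypothesis within Aim 2A. A flat or worse result could not be read as lack of learning, and the size of any observed improvement could not be read as the size of the skill gain.

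**Working it through.** **1. What the plan provides.** Three facts are explicit: the outcomes come from ordinary early and late sessions (section 4.2.1), those sessions get harder weekly (Specific Aims), and they are adapted to the child (section 5). The possible safeguards are as follows.

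- Common course for these outcomes: none stated.
- Difficulty as a covariate: none stated in section 7.
- Scaling of errors by distance or number of obstacles: none stated.
- Scaling of bouts: by driving time, which does not adjust for difficulty.
- Assistance: a percentage of time, so free of session length, but still dependent on how hard the course is.
- Navigation test in section 7: named once, undefined, and linked only to kinematic outcomes.

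**2. Errors in one child.** Let n be the opportunities for error in a session (turns, obstacles) and p the chance of error at each. Expected errors are n × p. If training cuts p by a fraction g, then

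late/early error ratio = (1 − g) × (n_late / n_early),

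which equals 1 when n_late / n_early = 1 / (1 − g). The documents give neither g nor n, so the values below are assumed.

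| True cut in p | Break-even opportunity ratio | Observed ratio at 1.5 times | Observed ratio at 2 times |
|---|---|---|---|
| 20% | 1.25 | 1.20 | 1.60 |
| 30% | 1.43 | 1.05 | 1.40 |
| 40% | 1.67 | 0.90 | 1.20 |
| 50% | 2.00 | 0.75 | 1.00 |

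Any observed ratio above 1 shows worsening in a child who improved.

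**3. Session length alone.** Section 5 allows 20 to 30 minutes, a range of 30/20 = 1.5. If the outcome is a count per session and opportunities scale with time, a true 30% cut can appear as 0.7 × 1.5 = 1.05, a 5% rise. If the outcome is a rate per minute, this part disappears and only the difficulty part remains. The wording does not settle which is meant.

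**4. With chance variation.** Assume 20 early errors, Poisson counts and a true 30% cut. The late mean is 14 times the difficulty ratio.

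| Difficulty ratio | Late mean | Chance that the late count exceeds the early count |
|---|---|---|
| 1 | 14 | 13% |
| 1.5 | 21 | 53% |
| 2 | 28 | 86% |
| 3 | 42 | 99.7% |

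**5. Group level.** The plan gives no figure for the navigation outcomes. Its only power figure is 82% in section 8, for 15 children, effect size 0.80 and two-sided alpha 0.05. A paired t-test with 14 degrees of freedom and noncentrality 0.80 × √15 gives 82.1%, so the figure is reproduced as a single two-time-point contrast. Use that as a yardstick: keep the true gain at 0.80 SD of change and subtract an assumed difficulty shift.

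| Shift (SD of change) | Apparent effect | Chance of a significant improvement |
|---|---|---|
| 0 | 0.80 | 82.1% |
| 0.2 | 0.60 | 58.0% |
| 0.4 | 0.40 | 30.3% |
| 0.6 | 0.20 | 10.8% |
| 0.8 | 0.00 | 2.5% |

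At a shift of 1.2 SD the chance of a significant worsening is 30.3%. Steps 2 to 5 show what the mechanism can do over assumed ranges. They do not estimate what it does in this trial.

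**The case against.** The strongest reply is that the damage is limited and partly recoverable. These are secondary process measures in a pilot. A harder late course mostly works against the hypothesis, so an observed improvement would tend to be conservative. Much of this stands: the main risk is a missed or understated gain. The direction is not guaranteed, however, because surfaces may differ and an easier one could flatter the late session.

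Four stronger readings are tempting, and the documents do not support them.

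- *Early bumps are zero by construction because training starts on a straight path.* Section 5 puts free play and structured games, with obstacle courses among the examples, in each session. No passage describes an early session without obstacles.
- *Only the bouts are normalised.* Assisted driving is already a percentage of time, and the wording for deviations and bumps may mean a within-session rate. Neither removes the difficulty problem.
- *The driving-skill question cannot be answered from these data.* Free play occurs in every session, the toys record speed, operating time and motion path (section 3), and trainers log delivery (section 5). Matched segments may therefore exist. If the navigation test proves to be a constant course, its kinematic outcomes are protected.
- *The distortion is largest in the children who progress most.* This is a plausible inference from tailoring, but no rule in the plan says that faster learners receive harder courses.

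None of this supplies a common task for assistance, bouts, deviations or bumps as the plan now stands.

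**Conclusion.** The point holds for the Aim 2A comparison of assistance, bouts, deviations and bumps. As written, early-to-late change in these measures cannot be separated from the planned change in task. This rests on explicit text, not on the illustrations.

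Its size in this trial cannot be calculated. Under the assumed multiplicative model, a 1.25- to 2-fold rise in opportunities is enough to cancel true error reductions of 20% to 50%.

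The point does not extend to QUEST, SHUEE, ABILHAND-Kids or the reach-grasp kinematics, none of which is measured on the training course. It should be corrected, because a stated hypothesis depends on it and the means of repair are largely in place.

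**What to change.** **Children whose early session is still ahead.** In sections 4.2.1 and 7, define the navigation test as one fixed course, with the same layout, obstacles, toy speed setting and prompting for a given child, driven in the early and the late coded session. Compute assistance, bouts, deviations and bumps for the Aim 2A comparison on that course only.

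**Children already finished or past the early session.** Compare only matched segments present in both sessions, such as free play or the same path type, on a like surface where possible. Express deviations and bumps per metre driven, from the motion-path sensor, or per obstacle. Label whole-session error rates as descriptive.

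**Wording.** State whether the error rate is per session or per unit of time or distance. Add deviations and bumps to the section 7 list. Reconcile early and late (section 4.2.1) with early, mid and late (section 7).

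**Cost.** The progress report in the IRB re-approval form gives data collection as complete for 12 children, with 4 in progress (2 of them in the control phase) and enrolment open. The fixed course therefore reaches only a few children, at a few minutes of session time each. For most of the sample the work is re-coding existing video, and some children may have no matched segments. No new staff or equipment is needed.
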